15.5. Quality of Life Analysis

Quality of Life (QoL) analyses will be performed for the safety population.

15.5.1. Variables & Derivations

15.5.1.1. EuroQol Five Dimensions Questionnaire (EQ-5D) scores

The EQ-5D is made up of two components, health state description and overall health evaluation.

In the description part, health status is measured in terms of five dimensions (5D):

1. Mobility dimension asks about the person's walking ability
 1. I have no problems walking
 2. I have slight problems walking
 3. I have moderate problems walking
 4. I have severe problems walking
 5. I am unable to walk
2. Self-care dimension asks about the ability to wash or dress by oneself
 1. I have no problems washing or dressing myself
 2. I have slight problems washing or dressing myself
 3. I have moderate problems washing or dressing myself
 4. I have severe problems washing or dressing myself
 5. I am unable to wash or dress

3. Usual activities dimension measures performance in “work, study, housework, family or leisure activities”
 1. I have no problems doing my usual activities
 2. I have slight problems doing my usual activities
 3. I have moderate problems doing my usual activities
 4. I have severe problems doing my usual activities
 5. I am unable to do my usual activities
4. Pain/discomfort dimension, it asks how much pain or discomfort they have
 1. I have no pain or discomfort
 2. I have slight pain or discomfort
 3. I have moderate pain or discomfort
 4. I have severe pain or discomfort
 5. I have extreme pain or discomfort
5. Anxiety/depression dimension, it asks how anxious or depressed they are
 1. I am not anxious or depressed
 2. I am slightly anxious or depressed
 3. I am moderately anxious or depressed
 4. I am severely anxious or depressed
 5. I am extremely anxious or depressed

The respondents self-rate their level of severity for each dimension using a 5-level scale: no problems, slight problems, moderate problems, severe problems and extreme problems.

In addition, the respondents evaluate their overall health status using the visual analogue scale. This scale is numbered from 0 to 100. 0 means the worst health you can imagine and 100 means the best health you can imagine.

15.5.1.2. Clinical Global Impression (CGI) – Improvement

The CGI-I scale is a 7-point scale that requires an approved rater to assess how much the patient's illness has improved or worsened relative to a baseline state at the beginning of the intervention and rated as:

1. Very Much Improved
2. Much Improved
3. Minimally Improved
4. No Change
5. Minimally Worse
6. Much Worse
7. Very Much Worse

15.5.1.3. Patient Global Impression of Change (PGIC)

The PGIC is a 7-point scale that requires the subject to assess the change (if any) in activity limitations, symptoms, emotions and overall quality of life.

The subject responses include:

1. No change (or condition has gotten worse)
2. Almost the same, hardly any change at all
3. A little better, but no noticeable change
4. Somewhat better, but the change has not made any real difference
5. Moderately better, and a slight but noticeable change
6. Better, and a definite improvement that has made a real and worthwhile difference
7. A great deal better, and a considerable improvement that has made all the difference

15.5.1.4. Quality of Life in Epilepsy-Patient-Weighted (QOLIE-31-P)

The QOLIE-31-P contains seven multi-item scales that investigate the following health concepts:

1. Emotional Well-Being

2. Social Functioning
3. Energy/Fatigue
4. Cognitive Functioning
5. Seizure Worry
6. Medication Effects
7. Overall Quality of Life (QOL)

The QOLIE-31-P overall score is obtained by using a weighted average of the multi-item scale scores. The QOLIE-31-P also includes a single item that assesses overall health on a visual analogue scale. The recorded responses will be converted to 0 -100-point scales as described in Table 3. The mean of the individual item scores in each subgroup are then calculated, with higher converted scores reflecting better quality of life. If one item within a scale score is missing, it will be replaced by the mean value of the other items. If more than one item is missing, the scale score will not be calculated.

The QOLIE-31-P overall score is obtained by using a weighted average of the 7 scale scores according to the following formula:

$$\begin{aligned} \text{Overall score} = & \text{Seizure worry} * 0.08 \\ & + \text{Overall quality of life} * 0.14 \\ & + \text{Emotional well-being} * 0.15 \\ & + \text{Energy/fatigue} * 0.12 \\ & + \text{Cognitive functioning} * 0.27 \\ & + \text{Medication effects} * 0.03 \\ & + \text{Social functioning} * 0.21 \end{aligned}$$

Table 3: QOLIE-31 Response Conversions

Scale	Response	Formula

Item Numbers	1	2	3	4	5	6	
Seizure Worry							
11.	0	20	40	60	80	100	$((\text{Resp-1})/(\text{Max-1})*100$
21.	0	33.3	66.7	100	-	-	$((\text{Resp-1})/(\text{Max-1})*100$
22.	0	50	100	-	-	-	$((\text{Resp-1})/(\text{Max-1})*100$
23.	0	33.3	66.7	100	-	-	$((\text{Resp-1})/(\text{Max-1})*100$
25.	100	75	50	25	0	-	$100 - ((\text{Resp-1})/(\text{Max-1})*100$
Overall Quality of Life							
1.	Multiply response by 10						
14.	100	75	50	25	0	-	$100 - ((\text{Resp-1})/(\text{Max-1})*100$
Emotional Well-being							
3.	0	20	40	60	80	100	$((\text{Resp-1})/(\text{Max-1})*100$
4.	0	20	40	60	80	100	$((\text{Resp-1})/(\text{Max-1})*100$
5.	100	80	60	40	20	0	$100 - ((\text{Resp-1})/(\text{Max-1})*100$
7.	0	20	40	60	80	100	$((\text{Resp-1})/(\text{Max-1})*100$

9.	100	80	60	40	20	0	$100 - ((\text{Resp-1}) / (\text{Max-1})) * 100$
Energy/Fatigue							
2.	100	80	60	40	20	0	$100 - ((\text{Resp-1}) / (\text{Max-1})) * 100$
6.	100	80	60	40	20	0	$100 - ((\text{Resp-1}) / (\text{Max-1})) * 100$
8.	0	20	40	60	80	100	$((\text{Resp-1}) / (\text{Max-1})) * 100$
10.	0	20	40	60	80	100	$((\text{Resp-1}) / (\text{Max-1})) * 100$
Cognitive Functioning							
12.	0	20	40	60	80	100	$((\text{Resp-1}) / (\text{Max-1})) * 100$
15.	0	33.3	66.7	100	-	-	$((\text{Resp-1}) / (\text{Max-1})) * 100$
16.	0	20	40	60	80	100	$((\text{Resp-1}) / (\text{Max-1})) * 100$
17.	0	20	40	60	80	100	$((\text{Resp-1}) / (\text{Max-1})) * 100$
18.	0	20	40	60	80	100	$((\text{Resp-1}) / (\text{Max-1})) * 100$
26.	100	75	50	25	0	-	$100 - ((\text{Resp-1}) / (\text{Max-1})) * 100$
Medication Effects							
24.	0	33.3	66.7	100	-	-	$((\text{Resp-1}) / (\text{Max-1})) * 100$
29.	100	75	50	25	0	-	$100 - ((\text{Resp-1}) / (\text{Max-1})) * 100$

30.	100	75	50	25	0	-	$100 - ((\text{Resp-1}) / (\text{Max-1})) * 100$
Social Functioning							
13.	0	20	40	60	80	100	$((\text{Resp-1}) / (\text{Max-1})) * 100$
19.	0	25	50	75	100	-	$((\text{Resp-1}) / (\text{Max-1})) * 100$
20.	0	25	50	75	100	-	$((\text{Resp-1}) / (\text{Max-1})) * 100$
27.	100	75	50	25	0	-	$100 - ((\text{Resp-1}) / (\text{Max-1})) * 100$
28.	100	75	50	25	0	-	$100 - ((\text{Resp-1}) / (\text{Max-1})) * 100$

Resp=Response, Max=Maximum possible response for the respective item.

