6.3. Other Endpoints

- Changes from baseline in the Neurological Disorders Depression Inventory for Epilepsy (NDDI-E)-6-item questionnaire.
- Changes from baseline in the Profile of Mood States Short-form (POMS-SF).
- Changes from baseline in the agitation/behavioral measurements as evaluated by the Modified Overt Aggression Scale (MOAS).
- Changes from baseline in Quality of Life in Epilepsy-Patient-Weighted (QOLIE-31-P) scores.
- Change from baseline in EuroQol Five Dimensions Questionnaire (EQ-5D) scores.
- Clinical Global Impression of Improvement (CGI-I) scores at each evaluation time point.
- Patient's Global Impression of Change (PGI-C) scores at each evaluation time point.

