11.4.4. Quality of Life in Epilepsy-Patient-Weighted

The QOLIE-31-P contains seven multi-item scales that investigate the following health concepts: emotional well-being, social functioning, energy/fatigue, cognitive functioning, seizure worry, medication effects and overall QOL. The QOLIE-31-P overall score is obtained using a weighted average of the multi-item scale scores.

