11.5.2. Titration Phase: Visit 2 (Week 1, Day 1)

- Review of inclusion/exclusion criteria.
- Record concomitant medications.
- Obtain vital signs and body weight.
- For females of childbearing potential, obtain sample for urine pregnancy test (to be confirmed with serum pregnancy test if positive).
- Record LAEP.
- Record AEs.
- Dispense study drug.
- Collect paper seizure diary.
- Distribute paper seizure diary.
- Review seizure diaries.
- Administer questionnaires (EQ-5D, QOLIE-31, POMS-SF, NDDI-E, MOAS, and eC-SSRS).

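### The quality-of-life endpoint is named patient-weighted (QOLIE-31-P), but the SAP scores its overall score with one fixed set of weights and a QOLIE-31 table

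*SAP*

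**What the plan says.** Protocol 6.3 lists the endpoint as "Changes from baseline in Quality of Life in Epilepsy-Patient-Weighted (QOLIE-31-P) scores", and SAP 2.4.3 repeats it. Protocol 11.4.4, whose heading carries the patient-weighted name, gives the only scoring rule in the protocol: "The QOLIE-31-P overall score is obtained using a weighted average of the multi-item scale scores". It does not say where the weights come from.

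SAP 15.5.1.4 supplies them: "The QOLIE-31-P overall score is obtained by using a weighted average of the 7 scale scores according to the following formula". The constants are 0.08 (seizure worry), 0.14 (overall quality of life), 0.15 (emotional well-being), 0.12 (energy/fatigue), 0.27 (cognitive functioning), 0.03 (medication effects) and 0.21 (social functioning). Responses are converted to 0-100 with "Table 3: QOLIE-31 Response Conversions". The same section notes that "The QOLIE-31-P also includes a single item that assesses overall health on a visual analogue scale".

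On administration, Protocol 11.5.2 reads "Administer questionnaires (EQ-5D, QOLIE-31, POMS-SF, NDDI-E, MOAS, and eC-SSRS". Sections 11.5.6, 11.5.10 and 11.5.11 also say QOLIE-31. Protocol Table 2 and the schedule in SAP 3.5 say QOLIE-31-P. SAP 3.4.2, on changes from the protocol's analyses, mentions only dose counts and average daily dose.

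**The concern.** A score that uses identical constants for everyone contains no weighting by the patient, whatever its name. Two explanations are possible. The form may be the plain QOLIE-31, in which case the endpoint carries the wrong name. Or the form may collect patient weights, in which case the SAP has no step that uses them. The mixed naming in the visit lists and schedules leaves this open.

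What is at stake is the accuracy of a reported result. Quality of life is part of a secondary objective (Protocol 5.2, SAP 2.2). Protocol 4.2 presents the quality-of-life assessments as new information beyond the Phase 3 program. The overall score also has its own change-from-baseline figure (SAP 15.5.2.4). A reader of the study report would take a patient-weighted label at face value.

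**Working it through.** **1. Is the SAP formula sound as a fixed-weight score?** The weights sum to 0.08 + 0.14 + 0.15 + 0.12 + 0.27 + 0.03 + 0.21 = 1.00, so the overall score stays on 0-100. The conversion (Resp - 1)/(Max - 1) × 100 gives 0/50/100 for three response levels, 0/33.3/66.7/100 for four, steps of 25 for five and steps of 20 for six. The reversed form gives the same values in descending order. All of these match Table 3. The formula is internally consistent.

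**2. Does any patient response set a weight?** Items per scale in Table 3:

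| Scale | Item numbers | Count |
|---|---|---|
| Seizure worry | 11, 21, 22, 23, 25 | 5 |
| Overall quality of life | 1, 14 | 2 |
| Emotional well-being | 3, 4, 5, 7, 9 | 5 |
| Energy/fatigue | 2, 6, 8, 10 | 4 |
| Cognitive functioning | 12, 15, 16, 17, 18, 26 | 6 |
| Medication effects | 24, 29, 30 | 3 |
| Social functioning | 13, 19, 20, 27, 28 | 5 |

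The total is 30: items 1 to 30, each used once as scale content. Adding the overall-health visual analogue item gives 31, which matches the 31-item description in both abbreviation lists. No item described in the SAP supplies a weight, and its missing-item rule covers scale items only.

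**3. Names side by side.**

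| Place | Name used |
|---|---|
| Protocol 6.3, 11.4.4; SAP 2.4.3, 15.5.1.4 (heading and formula), 15.5.2.4 | QOLIE-31-P |
| Protocol Table 2; SAP 3.5 schedule | QOLIE-31-P |
| Protocol 11.5.2, 11.5.6, 11.5.10, 11.5.11 | QOLIE-31 |
| SAP Table 3 title | QOLIE-31 |

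**4. How much can the choice of weights matter?** The documents give no patient weights, so this is illustration only. Suppose seizure worry and medication effects each improve by 30 points and nothing else changes. The overall change is 30 times the combined weight of the two scales.

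- SAP constants: 30 × (0.08 + 0.03) = 3.3 points.
- Equal weights (assumed): 30 × 2/7 = 8.6 points.
- Half the total weight on these two scales (assumed): 30 × 0.5 = 15 points.

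The effect need not go in one direction. For a 20-point gain in cognitive functioning alone, the SAP constants give 20 × 0.27 = 5.4 points, while equal weights give 20/7 = 2.9.

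**The case against.** The strongest reply is that the protocol promises only a weighted average of the scale scores, and the SAP formula is one. No section says that the weights come from the subject, which items would supply them or how they would enter. The case rests on the words in the instrument's name. This limits how far the point can go, but it does not remove it. SAP 15.5.1.4 is the only place where the weights are defined, and it defines them as constants under a patient-weighted heading.

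A reader might infer that patient weights are being collected and thrown away, or that the score is certainly not the one intended. The documents do not show this. Table 3 is a conversion table and not an inventory of the form; it already leaves out the visual analogue item. The count of 31 content items fits a plain QOLIE-31 at least as well, and in that case the defect is one of naming.

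A reader might also infer that the results could not be compared with other QOLIE-31-P studies. That depends on how those studies scored the instrument, which neither document states, so it is not part of this point.

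Finally, the consequence is limited. This is one of seven endpoints in its group, summarized descriptively with no testing (SAP 6.6). SAP 15.5.2.4 reports the subscale scores and their changes by arm and lists the individual items, so movement in any one scale is visible apart from the overall score. That stands in full.

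**Conclusion.** The plan is wrong as written on a narrow matter: whichever form is in use, following the SAP would report a fixed-weight overall score as patient-weighted. That conclusion rests only on the endpoint's name and the formula. Which of the two needs correcting depends on the form, and the documents do not settle that.

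The numerical effect in this trial is unknown. The spread of 3.3, 8.6 and 15 points shows sensitivity under assumed weights and an assumed pattern of change; it is not an estimate of bias. The point concerns the overall score and its figure. It identifies no error in the subscale scores, and the primary retention endpoint and the sample size are untouched. It should be corrected, but it does not threaten the study's main result.

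**What to change.** Confirm which questionnaire is administered, and settle the following before database lock so that the weighting is not chosen after open-label results are known.

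- If the form is QOLIE-31-P and it collects patient weights, replace the fixed-weight formula for the overall score in SAP 15.5.1.4 with the instrument's patient-weighted scoring. Name the items that supply the weights and state what happens when a weight is missing. Keep the fixed-weight score as a supplementary display.
- If the form is QOLIE-31, rename the endpoint and all outputs QOLIE-31 throughout and record the change in SAP 3.4.2. The formula and Table 3 can then stay as they are.
- In either case, make Protocol 11.5.2, 11.5.6, 11.5.10 and 11.5.11 agree with Protocol Table 2 and SAP 3.5.

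The cost is wording and at most one derivation program. No new data are needed if the weights are already collected.

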15.5.1.5. Profile of Mood States Short-form (POMS-SF)

The POMS-SF is an instrument designed to assess transient, distinct mood states and consists of a list of 37 adjectives. Respondents indicate the degree to which each adjective describes themselves during the last week using a 5-point Likert scale: 0= not at all, 1=a little, 2=moderately, 3=quite a bit, and 4=extremely. This format yields both an overall Total Mood Disturbance score as well as scores for each of the six subscales contained in the original POMS:

The items included in 6 subscales are

1. Fatigue-Inertia: worn-out, fatigued, exhausted, weary, bushed
2. Vigor-Activity: lively, active, energetic, cheerful, full of pep, vigorous
3. Tension-Anxiety: Tense, on edge, uneasy, restless, nervous, anxious
4. Depression-Dejection: unhappy, sad, blue, hopeless, discouraged, miserable, helpless, worthless

5. Anger-Hostility: angry, peeved, grouchy (written as grovely in some versions), annoyed, resentful, bitter, furious
6. Confusion-Bewilderment: confused, unable to concentrate, bewildered, forgetful, uncertain about things

Each subscale will be calculated by summing the point for items. The total mood disturbance score will be calculated by summing the total for the negative subscales and then subtracting the total for the positive subscale: Depression-Dejection + Tension-Anxiety + Anger-Hostility + Fatigue-Inertia + Confusion-Bewilderment -Vigor-Activity + 100. A constant (e.g. 100) will be added to total mood score in order to eliminate negative scores.

15.5.1.6. Neurological Disorders Depression Inventory for Epilepsy (NDDI-E)

The NDDI-E is a 6-item questionnaire validated to screen for depression in people with epilepsy. The NDDI-E consists of the following items:

1. Everything is a struggle
2. Nothing I do is right
3. Feel guilty
4. I'd be better off dead
5. Frustrated
6. Difficulty finding pleasure

Each item is rated on a 4-point Likert scale (1=never, 2=rarely, 3=sometimes, 4=always or often) with higher scores indicating a more severe response. Total Score is defined as the summation of all individual item scores. NIDDI-E scores ≥ 16 are considered positive for depression².

15.5.1.7. Modified Overt Aggression Scale (MOAS)

The MOAS is divided in four domains: 1. verbal aggression, 2. aggression against objects, 3 aggression against self, and 4 aggression against other people. A score from 0 to 4 is assigned to each act: 0 indicates no aggressive behavior and higher scores indicate increasing severity.

Section scores are weighted as follows: Scores from the “Verbal Aggression” section multiplied by 1; Scores from the “Aggression Against Property” section multiplied by 2; Scores from the “autoaggression” section multiplied by 3; Scores from the “physical aggression” section multiplied by 4. Weighted scores are then added together to get the total score. Total scores on the MOAS range from 0 to 40, with a higher score indicating more aggressive behavior.

Verbal Aggression:

0. No verbal aggression
1. Shouts angrily, curses mildly, or makes personal insults
2. Curses viciously, is severely insulting, has temper outbursts
3. Impulsively threatens violence toward others or self
4. Threatens violence toward others or self repeatedly or deliberately (e.g., to gain money or sex)

Aggression Against Property:

0. No aggression against property
1. Slams door angrily, rips clothing, urinates on floor
2. Throws objects down, kicks furniture, defaces walls
3. Breaks objects, smashes windows
4. Sets fires, throws objects dangerously

Autoaggression:

0. No autoaggression
1. Picks or scratches skin, pulls hair out, hits self (without injury)
2. Bangs head, hits fists into walls, throws self on floor

3. Inflicts minor cuts, bruises, burns or welts on self
4. Inflicts major injury on self or makes a suicide attempt

Physical Aggression:

0. No physical aggression
1. Makes menacing gestures, swings at people, grabs at clothing
2. Strikes, pushes, scratches, pulls hair of others (without injury)
3. Attacks others, causing mild injury (bruises, sprains, welts, etc.)
4. Attacks others, causing serious injury (fracture, loss of teeth, deep cuts, loss of consciousness, etc.)

15.5.2. Analysis of QOL Variables

15.5.2.2. Analysis of EuroQol Five Dimensions Questionnaire (EQ-5D)

The EQ-5D overall health status, visual analogue scale (VAS) scores, observed and changes from baseline for each evaluation time point will be summarized descriptively by arm.

The number and percentage of subjects for each health state description will be summarized by each evaluation timepoint and Arm. In addition shift table for each evaluation time point will be summarized by arm.

Figure of the mean (+/-SD) change from baseline for overall health (VAS) scores will be provided.

Listing of EQ-5D scores including score of each individual item will be provided.

15.5.2.2. Analysis of Clinical Global Impression of Improvement (CGI-I)

Frequency and percentage of Clinical Global Impression of Improvement (CGI-I) scores at each evaluation time point will be summarized by arm.

Listing of CGI-I scores will also be provided.

15.5.2.3. Analysis of Patient's Global Impression of Change (PGI-C)

Frequency and percentage of Patient's Global Impression of Change (PGI-C) scores for each evaluation time point will be summarized by arm.

Listing of PGI-C scores will also be provided.

15.5.2.4. Analysis of Quality of Life in Epilepsy-Patient-Weighted (QOLIE-31-P)

The QOLIE-31-P overall scores, global assessment and subscale scores, observed and changes from baseline in the score for each evaluation time point will be summarized descriptively by arm.

Figure of the mean (+/-SD) change from baseline for the total score by time point and arm will be provided.

Listing of QOLIE-31-P scores including each individual scoring item will be provided.

15.5.2.5. Analysis of Profile of Mood States Short-form (POMS-SF)

The POMS-SF total mood disturbance scores and subscale scores, observed and changes from baseline in the score of each evaluation time point will be summarized descriptively.

Figure of the mean (+/-SD) change from baseline for the total mood disturbance score by time point and arm will be provided.

Listing of POMS-SF scores including score of each individual item will be provided.

15.5.2.6. Analysis of Neurological Disorders Depression Inventory (NDDI-E)

The NDDI-E total scores and individual item scores, observed and changes from baseline in the score of each evaluation time point will be summarized descriptively.

The number of subjects with total score <16 and ≥ 16 will be presented by time point and arm.

Figure of the mean (+/-SD) change from baseline for the total score by time point and arm will be provided.

Listing of NDDI-E scores will also be provided.

15.5.2.7. Analysis of Modified Overt Aggression Scale (MOAS)

The MOAS total scores and domain scores, observed and changes from baseline for each evaluation time point will be summarized descriptively by arm.

Figure of the mean (+/-SD) change from baseline for the total score by time point and arm will be provided.

Listing of MOAS scores including score of each individual item will be provided.

16. Safety Outcomes

All outputs for safety outcomes will be based on the safety population.

16.1. Pre-treatment and Adverse Events

Pre-treatment events will be monitored from the time informed consent form (ICF) is provided up until the date of first ESL dose.

AEs will be monitored from the date of first ESL dose.

Serious adverse events will be monitored from the time informed consent/assent is obtained.

All AEs will be coded using Medical Dictionary for Regulatory Activities (MedDRA) version 13.1.

AEs are untoward medical occurrences:

- that occurred on or after the first dose of study medication.
- with a missing start date and a stop date on or after the first dose of study medication, OR
- with both a missing start and stop date.

See Appendix 2 for handling of partial dates for AEs.

16.1.1. **All AEs**

Incidence of AEs and number of events will be presented by arm, System Organ Class (SOC) and Preferred Term (PT). AEs will be presented by maximum severity and relationship to study medication as specified in the sections below.

For subject incidence summaries, each subject will be counted only once within each SOC and within each PT. All AEs will be summarized overall and by age group, race group, gender, baseline AEDs and number of baseline AEDs.

Listing of all AEs and pre-treatment AEs will be provided.

16.1.2. **Severity**

Severity is classed as mild/ moderate/ severe (increasing severity). AEs starting after the first dose of study medication with a missing severity will be classified as severe. If a subject reports an AE more than once within that SOC/ PT, the AE with the highest known severity will be used in the corresponding severity summaries.

